1.2 Purpose

The purpose of this study is to generate effectiveness data of ARNI, in the Chinese HFrEF patients with implanted ICD or CRT-D.

2 Objectives and endpoints

This study aims to explore the effect of ARNI on VA and ICD or CRT-D shocks and ATP. The objectives and related endpoints are further described in Table 2-1.

Table 2-1 Objectives and related endpoints

Objectives	Endpoints			
Primary Objective	Endpoint for primary objective			
To assess the proportion of patients with VA events over 6 months of ACEI/ARB and 6 months of ARNI treatment	Proportion of patients with VA events over 6 months of ACEI/ARB and 6 months of ARNI treatment (VA events are defined as SVT, NSVT and PVC, ICD shock and ATP, the definitions of SVT, NSVT, PVC, ATP are as below)			

Ok	pjectives	Endpoints			
Se	condary Objectives	Endpoints for secondary objectives			
•	To assess the number of occurrences of VA events and ICD or CRT-D shocks over 6 months of ACEI/ARB and 6 months of ARNI treatment	Numbers of NSVT, SVT, PVC, ICD shock and ATP experienced by patients over 6 months of ACEI/ARB and 6 months of ARNI treatment			
•	To compare the changes in LVEF and NYHA level between ACEI/ARB and ARNI treatments	 LVEF (%) over 6 months of ACEI/ARB and 6 months of ARNI treatment NYHA level over 6 months of ACEI/ARB and 6 months of ARNI treatment 			
•	To compare the changes in the NT-proBNP level between ACEI/ARB and ARNI treatments	NT-proBNP (pg/mL) level over 6 months of ACEI/ARB and 6 months of ARNI treatment			
•	To compare the healthcare resource utilization of HF patients during ACEI/ARB and ARNI treatments	Number of hospitalizations for arrhythmia or HF related hospitalizations over 6 months of ACEI/ARB and 6 months of ARNI treatment			

Abbreviations: ACEI = angiotensin-converting enzyme inhibitor;

; ARB = angiotensin receptor blockers; ARNI = angiotensin receptor neprilysin inhibitor; ATP = anti-tachycardia pacing; CRT-D = cardiac resynchronization therapy-defibrillator; HF = heart failure; ICD = implantable cardioverter defibrillator; LVEF = left ventricular ejection fraction; NSVT = non-sustained ventricular tachycardia; NT-proBNP = N-Terminal prohormone of Brain Natriuretic Peptide; NYHA = New York Heart Association; PVC = premature ventricular contraction; SVT = sustained ventricular tachycardia; VA = ventricular arrhythmias

Note

Sustained ventricular tachycardia is defined as tachycardia with hemodynamic disorder or lasting for >30 seconds

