12.5 Analysis of secondary endpoints

12.5.1 Efficacy endpoints

Please refer to Section 2 for the secondary objectives. The corresponding secondary variables are listed below:

- 1. Paired numbers of VA (SVT and NSVT in separate), PVC, ICD and ATP over 6 months of ACEI/ARB treatment and 6 months of ARNI treatment
- 2. Change in LVEF from date of treatment initiation over 6 months of ACEI/ARB treatment and 6 months of ARNI treatment
- 3. Change of NYHA level over 6 months of ACEI/ARB treatment and 6 months of ARNI treatment
- 4. Change proportion of NT-proBNP from date of treatment initiation over 6 months of ACEI/ARB treatment and 6 months of ARNI treatment
- 5. Number of hospitalizations for all causes and HF related hospitalizations during ACEI/ARB and ARNI treatments

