12.5.2 Statistical model, hypothesis, and method of analysis

All the following analysis will be performed on the FAS and PP.

Analysis of change from date of treatment initiation after 6 months of treatment for paired quantitative endpoints

Variables involved are number of SVT experienced, number of NSVT experienced, number of hourly PVC experienced, number of ICD shocks experienced, number of ATP experienced and time duration of NSVT experienced.

For each variable, a summary table will be reported to show the changes from baseline to Month 3, and 6 post-indexing and changes from Month 6 to Month 9, and 12 post-indexing date. The changes will be summarized by mean, standard error, median, quartiles, minimum and maximum.

Amended Protocol Version 02 (Track changes)

The change from date of treatment in interested endpoint after 6 months of each treatment is calculated by taking the difference between value recorded at the date of first treatment intake and at the date of last treatment intake.

Normality will be checked for the changes calculated, if the data is parametric, paired t-tests will be performed; else if the data is non-parametric, Wilcoxon signed-rank test will be used.

Analysis of change from date of treatment initiation after 6 months of treatment for continuous endpoints

Variables involved are LVEF, NYHA and NT-proBNP.

For each variable, a summary table will be reported to show the changes from baseline to Month 3, and 6 post-indexing and changes from Month 6 to Month 9, and 12 post-indexing date. The changes will be summarized by mean, standard error, median, quartiles, minimum and maximum.

The change from date of treatment in interested endpoint after 6 months of each treatment is calculated by taking the difference between value recorded at the date of first treatment intake and at the date of last treatment intake.

Normality will be checked for the changes calculated, if the data is parametric, paired t-tests will be performed; else if the data is non-parametric, Wilcoxon signed-rank test will be used.

Other than that, the variables involved before and after the initiation of ARNI will also be analyzed using the same statistical method.

Note that NYHA is a qualitative variable, appropriate data transformation (to be described in Statistical Analysis Plan) will be used to convert it into quantitative form.

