4.1.2 Secondary endpoints

• Number of occurrences of VA

The episodes of VA events over 6 months of ACEI/ARB and 6 months of ARNI treatment will be measured.

• Left ventricular ejection fraction

Left ventricular ejection fraction (%) will be compared at baseline, Month 6 and EOS.

• NYHA level

NYHA level will be recorded by investigators and compared at baseline, Month 6 and EOS.

• NT-proBNP

The measurements of NT-proBNP will be obtained from serum and plasma. Samples will be obtained before patients take their morning study drug dose. NT-proBNP (pg/mL) will be compared between ACEI/ARB and ARNI treatments at baseline, Month 6 and EOS.

• Number of hospitalizations

Number of hospitalizations for arrhythmia or HF related hospitalizations will be recorded during ACEI/ARB and ARNI treatments.

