7.4.2 Efficacy analysis of secondary endpoints

The analysis will be based on the efficacy analysis set and the per protocol set.

- Paired numbers of VA (SVT and NSVT in separate), PVC, ICD or CRT-D shocks and ATP over 6 months of ACEI/ARB treatment and 6 months of ARNI treatment.
- Change in LVEF from date of treatment initiation over 6 months of ACEI/ARB treatment and 6 months of ARNI treatment.
- Change of NYHA level over 6 months of ACEI/ARB treatment and 6 months of ARNI treatment.
- Change proportion of NT-proBNP from date of treatment initiation over 6 months of ACEI/ARB treatment and 6 months of ARNI treatment.
- Number of hospitalizations for all causes and HF related hospitalizations during ACEI/ARB and ARNI treatments.
- Paired numbers of VA (SVT and NSVT in separate), PVC, ICD or CRT-D shocks and ATP over 3 months of ACEI/ARB treatment and 3 months of ARNI treatment.
- Number of hospitalizations for all causes and HF related hospitalizations during 3 months of ACEI/ARB and ARNI treatments.

Analysis of change from date of treatment initiation after 6 months of treatment (for paired quantitative endpoints)

Variables involved are number of SVT experienced, number of NSVT experienced, number of hourly PVC experienced, number of ICD or CRT-D shocks experienced, number of ATP experienced and time duration of NSVT experienced, as well as number of hospitalizations for

all causes and HF related hospitalizations.

The number of occurrences or duration of each variable within 3 months and 6 months and their changes from baseline will be descriptively analyzed by treatment group and compared between groups. The changes will be summarized by mean, standard error, median, quartiles, minimum and maximum. Because the baseline and post-treatment device data collection cycles are different, data will be standardized on a daily basis before the analysis of changes.

Normality will be checked for the values of each variable and changes calculated. If the data is parametric, paired t-tests will be performed; else if the data is non-parametric, Wilcoxon signed-rank test will be used.

Analysis of change from date of treatment initiation after 6 months of treatment (for continuous endpoints)

[figure not shown]
Variables involved are LVEF, NYHA and NT-proBNP.

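### The declared secondary endpoint is hospitalisation for arrhythmia or HF, but the analysis sections use all-cause and HF-related hospitalisation, so the declared composite and its arrhythmia part get no efficacy result of their own

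*Protocol*

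**What the plan says.** The secondary objective is broad: "To compare the healthcare resource utilization of HF patients during ACEI/ARB and ARNI treatments". It names no cause of admission.

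The endpoint set against it in protocol Table 2-1 is specific: "Number of hospitalizations for arrhythmia or HF related hospitalizations over 6 months of ACEI/ARB and 6 months of ARNI treatment". The protocol summary, protocol 8.3.2 and SAP 4.1.2 all carry the same definition; in the SAP it reads "Number of hospitalizations for arrhythmia or HF related hospitalizations will be recorded during ACEI/ARB and ARNI treatments".

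The analysis text differs. Protocol 12.5.1 refers back to Section 2 and presents its list as the variables that correspond to those objectives. Its fifth variable is "Number of hospitalizations for all causes and HF related hospitalizations during ACEI/ARB and ARNI treatments". SAP 7.4.2 has the same bullet for the 6-month window and adds "Number of hospitalizations for all causes and HF related hospitalizations during 3 months of ACEI/ARB and ARNI treatments".

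On testing, protocol 12.5.2 lists device counts and NSVT duration ("number of ICD shocks experienced, number of ATP experienced and time duration of NSVT experienced" closes that list), then LVEF, NYHA and NT-proBNP. It lists no hospitalisation variable. SAP 7.4.2 extends the list: "time duration of NSVT experienced, as well as number of hospitalizations for" all causes and HF. The method there is a paired t-test or a Wilcoxon signed-rank test.

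**The concern.** An endpoint should carry the same definition from the objectives table to the analysis section. Here it changes on the way, and the part that drops out by name is arrhythmia admission, the component closest to a trial about ventricular arrhythmia.

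Two things are at stake. First, the study report would give a result for an endpoint that Table 2-1 does not declare, and none for the one it does. Protocol 4.5 says the interim analysis will cover every endpoint in Section 2; on the readable text, that cannot be done for this one. Second, the SAP holds both definitions (4.1.2 and 7.4.2) in an open-label study whose interim efficacy set is already fixed at 117 subjects. A later decision to report one or the other would be hard to defend as prespecified.

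**Working it through.** There is no figure to reproduce: neither sample-size section gives a rate, effect size or power for hospitalisation. The check is a comparison of every statement about the endpoint.

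| Place | Role | Admissions named |
|---|---|---|
| Protocol summary | definition | arrhythmia or HF |
| Protocol Table 2-1 | definition | arrhythmia or HF |
| Protocol 8.3.2 | definition | arrhythmia or HF |
| SAP 4.1.2 | definition | arrhythmia or HF |
| Protocol 12.5.1 | analysis variable | all-cause; HF |
| Protocol 12.5.2 | variables given a test | none |
| SAP 7.4.2, 6-month bullet | analysis variable | all-cause; HF |
| SAP 7.4.2, 3-month bullet | analysis variable | all-cause; HF |
| SAP 7.4.2, tested-variable list | variables given a test | all-cause; HF |

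All four definition statements name arrhythmia. None of the analysis statements does. All of this is current text, not the amendment log.

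**Can the declared endpoint be recovered from the planned output?** For one patient and one period, write A, H and O for the numbers of admissions for arrhythmia, for HF and for anything else, each admission given one cause.

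- Declared: A + H. If the wording is read as two separate counts, it is A and H.
- Planned: T = A + H + O, and H.
- Available by subtraction: T − H = A + O.

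A stays mixed with O, so neither A nor A + H can be obtained. This is so whether the declared wording is read as a composite or as two counts.

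**What does O do to the all-cause comparison?** Let D be the within-patient difference, ARNI period minus ACEI/ARB period.

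- D(T) = D(A + H) + D(O)
- Mean: E[D(T)] = E[D(A + H)] + E[D(O)]
- Variance: Var[D(T)] = Var[D(A + H)] + Var[D(O)] + 2 Cov[D(A + H), D(O)]

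If unrelated admissions are equally frequent in both periods, E[D(O)] = 0 and the mean difference is unchanged. The variance rises by Var[D(O)], assuming the covariance is about zero, and power falls. If their frequency differs between periods, the mean shifts, in either direction. The documents give no admission rates, so neither effect can be given a number.

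**The case against.** The strongest reply is that all-cause admission suits the objective. The objective speaks only of resource utilisation, protocol 12.5.1 and SAP 7.4.2 agree with each other, and the documents do not show which wording is the slip. That much stands: all-cause may be what the sponsor wants. But the endpoint attached to the objective is stated the other way in four places, and protocol 12.5.1 says its list corresponds to Section 2. If the intent changed, the definition has to change with it.

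A reader might infer that arrhythmia admissions are never tested, or that the endpoint has no result at all. The documents do not support that. HF admissions are a named, tested variable in the SAP, and arrhythmia admissions are inside the tested all-cause count. Hospitalisation is also, with exceptions, a criterion for a serious adverse event, and the SAP tabulates those by organ class, preferred term and treatment. Arrhythmia admissions reported that way would be visible, though as patients rather than admissions and without an efficacy comparison.

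A reader might also infer that unrelated admissions pull the contrast between periods toward zero. For the planned paired difference this does not follow, as shown above; it would apply to a rate ratio or a standardised effect, and no ratio is planned for this endpoint.

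Finally, some exploratory sections are not available to read, so a further analysis there cannot be excluded. The endpoint is declared secondary, however, and the secondary analysis text is readable in both documents.

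**Conclusion.** The contradiction is certain and is carried into the SAP. Followed exactly, the plan tests all-cause and HF-related admissions and produces no separate efficacy result for the declared arrhythmia-or-HF endpoint or for its arrhythmia component. The protocol has a further gap, since 12.5.2 gives no hospitalisation variable a test and only the SAP supplies one.

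The size is limited: one of five secondary variables, with no stated power, and no effect on the primary analysis. The extra variance in the all-cause comparison is a secondary consequence of unknown amount, and the conclusion does not depend on it. Nor do the documents show that anyone would pick a definition after seeing data; they show only that both are open. The point should be corrected before the final analysis.

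This rests on two assumptions: that no unseen section analyses the declared endpoint, and that the table shells, which are separate documents, follow SAP 7.4.2.

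**What to change.** Use one definition throughout.

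- **Preferred, because it keeps the declared endpoint:** in protocol 12.5.1, protocol 12.5.2 and SAP 7.4.2, make hospitalisations for arrhythmia or HF the secondary variable, with each component shown, over the 6-month and 3-month windows. State its test in protocol 12.5.2 as well as in the SAP. Keep all-cause hospitalisation as an additional utilisation measure, labelled as such.
- **Alternative, if all-cause is intended:** change the definition in the protocol summary, Table 2-1, protocol 8.3.2 and SAP 4.1.2 by documented amendment before the final analysis, and still add the variable to protocol 12.5.2.

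The cost is small. Table 8-1 schedules hospital admission data at every visit, and the planned HF count already requires admissions to be classified by cause. One thing has to be confirmed first: the documents do not show that the CRF identifies arrhythmia admissions, and the review committee's stated remit is device events and serious adverse events, not causes of admission. If the CRF does not identify them, the cause would have to be classified from the admission records, under a rule written down before the analysis.

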12.5.2 Statistical model, hypothesis, and method of analysis

All the following analysis will be performed on the FAS and PP.

Analysis of change from date of treatment initiation after 6 months of treatment for paired quantitative endpoints

Variables involved are number of SVT experienced, number of NSVT experienced, number of hourly PVC experienced, number of ICD shocks experienced, number of ATP experienced and time duration of NSVT experienced.

For each variable, a summary table will be reported to show the changes from baseline to Month 3, and 6 post-indexing and changes from Month 6 to Month 9, and 12 post-indexing date. The changes will be summarized by mean, standard error, median, quartiles, minimum and maximum.

Amended Protocol Version 02 (Track changes)

The change from date of treatment in interested endpoint after 6 months of each treatment is calculated by taking the difference between value recorded at the date of first treatment intake and at the date of last treatment intake.

Normality will be checked for the changes calculated, if the data is parametric, paired t-tests will be performed; else if the data is non-parametric, Wilcoxon signed-rank test will be used.

Analysis of change from date of treatment initiation after 6 months of treatment for continuous endpoints

Variables involved are LVEF, NYHA and NT-proBNP.

For each variable, a summary table will be reported to show the changes from baseline to Month 3, and 6 post-indexing and changes from Month 6 to Month 9, and 12 post-indexing date. The changes will be summarized by mean, standard error, median, quartiles, minimum and maximum.

The change from date of treatment in interested endpoint after 6 months of each treatment is calculated by taking the difference between value recorded at the date of first treatment intake and at the date of last treatment intake.

Normality will be checked for the changes calculated, if the data is parametric, paired t-tests will be performed; else if the data is non-parametric, Wilcoxon signed-rank test will be used.

Other than that, the variables involved before and after the initiation of ARNI will also be analyzed using the same statistical method.

Note that NYHA is a qualitative variable, appropriate data transformation (to be described in Statistical Analysis Plan) will be used to convert it into quantitative form.

12.5.3 Safety endpoints

For all safety analyses, the SAF will be used and there will be no formal statistical inference analysis. All listings and tables will be presented by treatment group.

Safety summaries (tables and figures) include only data from the on-treatment period with the exception of baseline data which will also be summarized where appropriate (e.g. change from baseline summaries). In addition, a separate summary for death including on treatment and post treatment deaths will be provided. In particular, summary tables for AEs will summarize only on-treatment events, with a start date during the on-treatment period (treatment-emergent AEs).

Adverse events

All information obtained on AE will be displayed by treatment group and patient.

The number (and percentage) of patients with treatment-emergent AE (events started after the first dose of study medication or events present prior to start of double-blind treatment but increased in severity based on preferred term) will be summarized by treatment, primary system organ class, preferred term and maximum severity.

Separate summaries will be provided for study medication related AE, death, SAE, other significant AE leading to discontinuation and AE leading to dose adjustment.

The number and proportion of patients with AE as described in Section 10.1 will be summarized by treatment.

A patient with multiple AE within a primary system organ class is only counted once toward the total of the primary system organ class.

Adverse events which will be counted for a specific treatment period are those which are treatment-emergent. These events are those with an onset after the start of the treatment period, or which were present prior to the start of the treatment period but increased in severity, changed from being not suspected to being suspected of study drug relationship, or developed into SAEs after the start of the treatment period.

Vital signs

All vital signs data (see Section 8.4.2) will be listed by treatment group, patient, and visit/time and if ranges are available, abnormalities (and relevant orthostatic changes) will be flagged. Summary statistics will be provided by treatment and visit/time.

Clinical laboratory evaluations

All laboratory data (see Section 8.4.1) will be listed by treatment group, patient, and visit/time and if normal ranges are available abnormalities will be flagged. Summary statistics will be provided by treatment and visit/time. Shift tables will be used to compare baseline to the worst on-treatment value.

12.7 Interim analyses

An interim analysis will be conducted once half of the enrolled patients have completed the study.

12.8 Sample size calculation

12.8.1 Primary endpoint

McNemar Test is used in the primary analysis to test for 2 correlated proportions. Approximate formula from Machin et al (1997) is used to calculate the minimum size required.

For the proportion of discordant pairs, the following approximate formula is used:

Proportion Discordant =
$$P_t(1 - P_s) + P_s(1 - P_t)$$

where P_t and P_s are proportion of patients experiencing the event of interest during ACEI/ARB and ARNI treatment period respectively. Over here, both proportions are assumed to be similar to de Diego et al (2018)'s study. According to de Diego et al (2018)'s study, SVT (one of the VA event) has the following incidence 8/120 and 1/120 during ACEI/ARB and ARNI treatment period respectively. Hence, by substitute both into the equation above, proportion discordant calculated is 0.0739 after rounding off.

For the difference, a parameter under effect size is approximated by the following formula:

Effect Size =
$$P_t(1 - P_s) - P_s(1 - P_t)$$

and after substituting P_t and P_s defined above, the effect size calculated is -0.0583.

Thus, by considering the parameters defined above, power of 0.8 and significance level of 0.05, the sample size required is 175. Further consider a dropout rate of 20%, the minimum sample size required is 219.

The above calculation is calculated using PASS 11 software's Test for Two Correlated Proportion (McNemar Test) [Differences] procedure.

For proportion of patients had ICD or CRT-D shocks occurrence over 6 months of ACEI/ARB and 6 months of ARNI treatment, the above sample size will provide 95% - 98% power to detect a proportion difference of 0.075 at two-sided significance level of 0.05. The proportion difference is derived from the published literature (de Diego et al 2018).

